All samples will be barcoded, with data entered and stored in Labmatrix, the patient sample data management system utilized by the NCI Clinical Pharmacology Core (CPC). This is a secure program, with access to the Labmatrix system limited to defined CPC personnel who are issued individual user accounts. The program creates a unique barcode ID for every sample and sample box, which cannot be traced back to patients without Labmatrix access. The data recorded for each sample includes the patient ID, name, trial name/protocol number, sample collection time, cycle time point, dose, material type, as well as box and freezer locations. Patient demographics associated with the clinical center patient number are provided in the system. Samples will be stored until requested by the PI. All requests are monitored and tracked in Labmatrix.

**Table 4: Correlative Studies\***

PMBC	Plasma/Whole Blood	Archived Tissue Samples	Tumor and/or Effusion Cells
Immune phenotyping Dendritic cell maturation	TRAIL levels Serum M30 assay Serum M65 assay Cytokines Circulating Tumor Cells Cell free DNA Cell free Mitochondrial DNA	Whole exome sequencing RNASeq Markers of Apoptosis TRAIL expression TRAIL receptor expression Dopamine Receptor D2	Whole exome sequencing RNASeq Dopamine Receptor D2 Electron Microscopy

\* Correlative studies will include but are not limited to the studies listed above. Correlative studies will be performed if adequate samples are collected and on select patients.

## 5.2 GENOMIC ALTERATIONS IN BREAST AND ENDOMETRIAL CANCERS

Patients with breast or endometrial cancer who are being evaluated for treatment may have tumor tissue obtained through the course of work-up, diagnosis or staging of their disease. This tissue may be submitted from outside (i.e. FFPE tissue) or obtained during tests at the Clinical Center. This tumor tissue will be submitted to Frederick for next-generation DNA sequencing using comprehensive cancer gene panel testing. This tumor sequencing is exploratory and will not be reported to the patient. Germline testing will be performed with the sole purpose to help identify the somatic mutations. As many as 20 patient tumor samples will be sent for molecular profiling per year of the protocol. No exploratory germline testing will be performed on this protocol.

*Abbreviated Title: ONC201 in advanced cancers*

*Version Date: 06/17/2020*

Patients with endometrial cancer and associated malignant peritoneal cytology that is obtained at the time of staging laparoscopy will have that peritoneal fluid submitted for clinical diagnostic cytopathologic analysis in the Laboratory of Pathology. In addition, any peritoneal or pleural fluid collected during enrollment on the study will be examined for malignant cells in the Laboratory of Pathology's Cytopathology section.

### 5.3 TUMOR BIOPSIES

#### 5.3.1 Timing\*

Biopsies will be performed at the following times:

- Mandatory – after consent, prior to treatment on cycle 1 day 1
- Mandatory - cycle 2 day 2 (< 24 hours of ONC201 dose)
- Optional - at the time of progression

\*Biopsies may be not performed on the specific dates and times due to the following reasons, including but not limited to, delayed recovery of hematologic toxicities, delayed clinic schedule, or national holidays.

#### 5.3.2 Tissue Sampling and Handling

1. Attempts will be made to obtain up to four cores if safe and feasible. These tumor core biopsies will be obtained percutaneously or per vagina through interventional radiology (for endometrial cancer cohort) as long as considered minimal surgical risk. Two 3-millimeter punch biopsies of skin will be acceptable in lieu of 18-gauge core biopsies for patients with skin involvement. Inability to get tissue with a reasonable attempt will not preclude treatment and the patient will remain eligible for all other translational components.
  - a. Core 1: Electron Microscopy
  - b. Core 2: RNA later buffer
  - c. Cores 3: FFPE
  - d. Cores 4 and 5: OCT
2. The use of imaging to facilitate biopsies will be decided upon by members of the interventional radiology team. Should CT scans be needed for biopsy, a limit of 10 scans for each procedure will be observed to minimize radiation exposure to the patient.
3. The schedule for the biopsies will be made with Special Procedures ([name]). Members of the WMB lab will be on call to receive and embed biopsies: [[contact]](mailto:[contact]), [contact], beeper [name].

*Abbreviated Title: ONC201 in advanced cancers*

*Version Date: 06/17/2020*

4. All cores will be stored, barcoded, in the WMB lab at -80°C on site until use according to our laboratory SOP. See **Table 5** for information about specimen collection and storage.

#### 5.4 BLOOD SAMPLES

The following tests will be performed on selected patients' peripheral blood samples. If collected samples are not sufficient, the correlative studies will be performed in order of priority as detailed below. These correlative studies will be done in an exploratory fashion.

##### 5.4.1 **Timing**

Research blood samples will be performed at the following times:

- C1D1: after consent, prior to treatment on cycle 1 day 1
- C1D1: 6 hours after ONC201 administration (blood for PK only)
- On Day 1 of each cycle starting with cycle 2: Prior to treatment on day 1
- Optional - at the time of progression

##### 5.4.2 **Sampling and Handling**

5. We will collect no more than 40ml of research blood at each time point specified. If there is an issue obtaining blood from a participant, samples will be prioritized as follows:
  - a. 8ml of blood for immune assays (citrate blue/black tiger top)
  - b. 10 ml of blood for circulating tumor cells, cell free DNA and cell free mitochondrial DNA (cell save preservative)
  - c. 10ml of blood for germline DNA analysis for correlative studies (Streck tube; C1D1 only)
  - d. 4ml of blood for cytokine analysis (lavender top tube)
  - e. 6ml of blood each for serum M30/M65 and Trail expression (red top tube)
  - f. 6ml of blood for Pharmacokinetics (lavender top tube; C1D1 only but prior to drug ingestion and then 6 hours after)
6. Members of the WMB lab will be on call to receive patient samples: [[contact]](mailto:[contact]), [contact], beeper [name].
7. See **Table 5** for information about specimen collection and storage.
8. As soon as possible after the patient is scheduled please send an email notification to the [name] Lab, Developmental Therapeutics Branch, NCI: [name] at [[contact]](mailto:[contact]); [name] at [[contact]](mailto:[contact]); [name] at [[contact]](mailto:[contact])

*Abbreviated Title: ONC201 in advanced cancers*  
*Version Date: 06/17/2020*

[[contact]](mailto:[contact]) and [name] at [[contact]](mailto:[contact]) that the sample is scheduled. After the samples are drawn please call the [name] lab at [contact] to communicate that the sample is ready. Keep the sample on the unit at room temperature. The sample will be picked up by a lab member, entered in a secure patient database and processed for CTC assessment and immune subset analysis.

**Abbreviated Title:** ONC201 in advanced cancers  
**Version Date:** 06/17/2020

## 5.5 TABLE 5: SPECIMEN COLLECTION AND STORAGE

### Tumor Biopsy\*

Correlative Study	Collection Point(s)	SOP for collection	Contact	SOP after collection
Electron Microscopy	C1D1 prior to treatment  C2D2  Optional at time of progression	Preserve the biopsy tissue sample is to fix the tissue without delay 1. Prepare Eppendorf microfuge tube (~1.5ml) or conical centrifuge tube (15ml) fill with EM fixative (4% formaldehyde + 2% glutaraldehyde in 0.1M cacodylate buffer, ambient temperature) and drop the tissue into the fixative. 2. Fix for 2hrs at room temperature, then store in 4C. 3. Obtain barcode	Members of the WMB labs will be on call to receive and embed biopsies: [contact] , [contact], beeper [name].	Fix for 2hrs at room temperature, then store in 4C.  Will be shipped in batches to [name] for processing/embedding for the EM analysis.  [name] [name] [contact] [contact] EMAIL: [contact]
Dopamine Receptor D2  And  Death Receptors	C1D1 prior to treatment  C2D2  Optional at time of progression	a) Prepare two or three Eppendorf tubes which contain 1 ml of 4% formalin and leave tubes at room temperature. b) Quickly make your way to Interventional Radiology (IR) on the floor. Ask one of the techs or nurses where your patient is and prepare to receive the sample. c) Lay a paper towel next to your bucket. d) Take out the forceps and rinse/dry them thoroughly before placing them on the paper towel. e) Put on a mask, hair net and gloves.	Members of the WMB labs will be on call to receive and embed biopsies: [contact] , [contact], beeper [name]..	Oncocoetics requests: 5 unstained slides (FFPE) from each time point  Will later be shipped to Oncocoetics: [name] Biorespiratory Manager- Boston SciSafe, Inc [name] [name] [contact]

**Abbreviated Title:** ONC201 in advanced cancers  
**Version Date:** 06/17/2020

		
f) When the radiologist is ready, take the slide with the sample on it while being CAREFUL NOT TO TOUCH THE DOCTOR'S GLOVE.
 
g) Use the forceps to gently pickup and place the sample in the Eppendorf tube.
 
h) Leave the Eppendorf tube at room temperature overnight.
 
i) Next day carefully remove 4% formalin from the Eppendorf tube and replace 1 ml of 70% ethanol. Leave the tube at room temperature.
 
j) Call AmericanHistolab ([contact]) to pick up the sample.
 
k) Cost for paraffin embedding and H&E staining: \$7.95/block. Catalogue Number: 1001
 
l) The sample labelling with a random code and barcoding should be same as OTC preserved samples collected at the same day
		
Email: [contact]
 
At the time of shipment, the laboratory must complete the Specimen Shipping Form ( section 15.6.5) and email it to the following:
 
 
1. [contact]
 
a) [contact]
 

Whole Exome Sequencing and RNAseq done	
C1D1 prior to treatment
 
C2D2
 
Optional at time of progression
	
 
• Perform core needle biopsy.
 
• Pick the core from the biopsy needle onto a sterile glass slide.
 
• Fill cryomold about 1/3 full with OCT. Place the cryomold in dry ice to partially freeze the optimal cutting temperature (OCT). The OCT should be jelly-like, not completely frozen.
 
• Carefully lift the core biopsy by both ends with sterile forceps. Do not stretch the biopsy or it will break.
 
	
Members of the WMB labs will be on call to receive and embed biopsies: [contact], [contact], beeper [name].
	
 
3 Frozen sections should be cut at 5-8um on plain, uncoated glass microscope slides.
 
4 The tissue section should be placed as close as possible to the center of the slide. Do not place the frozen section at the end of the slide.
 
5 Two tissue sections from the same biopsy may be placed on the same glass slide if space permits.
 
6 Do not allow the tissue section to air on the slide. Freeze immediately on dry ice or
 

**Abbreviated Title:** *ONC201 in advanced cancers*  
**Version Date:** 06/17/2020

		
 
• Lay the biopsy as straight as possible in the OCT. Once the sample touches the OCT, you cannot reposition it or the sample will break apart.
 
• Quickly add OCT on top of the biopsy, completely covering the sample.
 
• Ensure the sample is level and freeze immediately in dry ice.
 
• Obtain barcode
 
 
Store wrapped in aluminum foil or in a 50ml Falcon tube at 70 degrees C.
		at- 80 degrees C.
--	--	----------------------------------------------------------------------------------------------------------------------------------------------------------------------------------------------------------------------------------------------------------------------------------------------------------------------------------------------------------------------------------------------------------------------------------------------------------------------	--	----------------------

\*Biopsies may be not performed on the specific dates and times due to the following reasons, including but not limited to, delayed recovery of hematologic toxicities, delayed clinic schedule, or national holidays.

#### Plasma/Serum

Correlative Study	Collection Point(s)	SOP for collection	Contact	SOP after collection
Pharmacokinetics	C1D1 prior to treatment	
 
1. Collect 6ml of blood into a Lavender top, vacutainer tube
 
2. Obtain barcode
 
	Members of the WMB labs will be on call to receive study samples: [contact] , [contact], beeper [name].	
 
1. Centrifuge the filled lavender top tube at 1500 g (3000 rpm) for 15 minutes until the plasma and the cells are well separated.
 
2. Label 2 blue cap transfer vials lengthwise with the appropriate barcode labels indicating “plasma (blue)”.
 
3. Clearly print the study number “Study XXX”, patient ID number, date and time of the blood draw.
 
4. Transfer ~1.5 mL of plasma into each of the 2 blue top transfer vials labeled “plasma (blue)”
 
5. Store sample in a freezer with a minimum -20°C or preferable -70°C
 

	C1D1 6hr after drug	Blood must be centrifuged, separated and frozen within 2 hours of collection. Specimens must be stored frozen at -70°C (preferred) or -20°C (acceptable) at each study site until shipped on dry ice to the designated analytical laboratory.		
	Optional at time of progression			

**Abbreviated Title:** *ONC201 in advanced cancers*  
**Version Date:** *06/17/2020*

Correlative Study	Collection Point(s)	SOP for collection	Contact	SOP after collection
Serum M30 and M65	
C1D1 prior to treatment
 
Day 1 of each subsequent cycle
 
Optional at time of progression
	
4. Collect 6ml of blood into a Red top, vacutainer tube
 
5. Obtain barcode
 
Blood must be centrifuged, separated and frozen within 2 hours of collection. Specimens must be stored frozen at -70°C (preferred) or -20°C (acceptable) at each study site until shipped on dry ice to the designated analytical laboratory.
	
Members of the WMB labs will be on call to receive study samples:  [contact], [contact], beeper [name].
	
Will later be shipped to Oncoceutics:
 
Sample Receiving Officer  XenoBiotic Laboratories, Inc  [name]  [name]  [contact] x252  Email: [contact]
 
At the time of shipment, the laboratory must complete the Specimen Shipping Form (15.6.5 Appendix E) and email it to the following:
 
m) [contact]  n) [contact]
 
 
1. Centrifuge the filled red top tube at 1500 g (3000 rpm) for 15 minutes until the plasma and the cells are well separated.
 
2. Label 2 yellow cap transfer vials lengthwise with the appropriate barcode labels indicating “serum (red)”.
 
3. Clearly print the study number “Study XXX”, patient ID number, date and time of the blood draw.
 
4. Transfer ~1.5 mL of serum into each of the 2 yellow top transfer vials labeled “serum (red)”
 
5. Store sample in a freezer with a minimum -20°C or preferable -70°C
 

**Abbreviated Title:** *ONC201 in advanced cancers*  
**Version Date:** *06/17/2020*

Correlative Study	Collection Point(s)	SOP for collection	Contact	SOP after collection
TRAIL Expression	C1D1 prior to treatment  Day 1 of each subsequent cycle  Optional at time of progression	
 
1. Collect 6ml of blood into a Red top, vacutainer tube
 
2. Obtain barcode
 
 
Blood must be centrifuged, separated and frozen within 2 hours of collection. Specimens must be stored frozen at -70°C (preferred) or -20°C (acceptable) at each study site until shipped on dry ice to the designated analytical laboratory.
	
Members of the WMB labs will be on call to receive study samples:  [contact], [contact], beeper [name].
	
See above Pharmacokinetics section for shipping information to Oncoceutics.
 
 
2. Centrifuge the filled red top tube at 1500 g (3000 rpm) for 15 minutes until the plasma and the cells are well separated.
 
3. Label 2 yellow cap transfer vials lengthwise with the appropriate barcode labels indicating “serum (red)”.
 
4. Clearly print the study number “Study XXX”, patient ID number, date and time of the blood draw.
 
5. Transfer ~1.5 mL of serum into each of the 2 yellow top transfer vials labeled “serum (red)”
 
6. Store sample in a freezer with a minimum -20°C or preferable -70°C
 
 
See above Pharmacokinetics section for shipping information to Oncoceutics.

Germline gDNA	C1D1	
 
1. Collect 10mL of blood into BCT Streck tubes ( Label the tube with appropriate Study/Patient Number Identifiers. Record the time of collection and whether the blood was drawn using a peripheral venous access device (eg. cannula
 
	
Members of the WMB labs will be on call to receive study samples:  [contact], [contact], beeper [name].
	
See Appendix D for full SOP

**Abbreviated Title:** *ONC201 in advanced cancers*  
**Version Date:** *06/17/2020*

Correlative Study	Collection Point(s)	SOP for collection	Contact	SOP after collection
Circulating Tumor Cells, Cell free DNA, and Cell free mitochondrial DNA	C1D1 prior to treatment	
or butterfly) or a central venous access device (CVAD).
 
 
2. After collection, gently invert tubes 8-10 times to mix and leave tubes upright prior to centrifugation.
 
3. Obtain barcode
 
		
As soon as possible after the patient is scheduled please send email notification to the [name] lab: [name] at [contact]; [name] at [contact]; [name] at [contact]; [name] at [contact] that the sample is scheduled.

	Day 1 of each subsequent cycle	
 
1. Either one 10-mL CellSave Preservative Tube OR a 10-mL Streck tube, PLUS one 10-mL CPT tube for each time point will be collected from each patient. Please, make sure tubes are full.
 
2. Immediately after collection, invert the blood tubes 3-4 times.
 
3. Plasma from these samples will be stored at [name] lab after CTCs are harvested.
 
4. Obtain barcode
 
		
As soon as the sample is drawn, please call the [name] lab at [contact] to communicate that the sample is ready. Keep the sample on the unit at room temperature. The sample will be picked up by the lab and processed for CTC enumeration.

Cytokine Analysis	C1D1 prior to treatment	
 
3. Collect 4ml of venous blood in a venous blood BD Vacutainer spray-coated K2EDTA (lavender top) tube.
 
4. Gently invert 10 times to mix blood and anticoagulant.
 
5. Store tubes at room temperature until centrifugation.
 
		
As soon as possible after the patient is scheduled please send email notification to the Blood Processing Core for processing and storage of the blood sampled (EDTA plasma) at [contact] - at least 24 hours before transporting samples (the Friday before is preferred). For sample pickup, page [name].

	Day 1 of each subsequent cycle			
For immediate help, call [contact] (main blood processing core number) or, if no answer, [contact] (main clinical pharmacology lab number). For questions regarding sample processing, contact [contact]
 
As soon as the sample is drawn, please call the BPC to communicate that the sample is ready. Keep the sample on the unit at room temperature.

	Optional at time of progression			
	Optional at time of progression			

**Abbreviated Title:** *ONC201 in advanced cancers*  
**Version Date:** *06/17/2020*

Correlative Study	Collection Point(s)	SOP for collection	Contact	SOP after collection
		It is generally preferred and often necessary to process the samples within 5 hours of collection.		Plasma will be separated and aliquoted according to the BPC SOPs and stored, barcoded, in the CPC repository until use (See Section 15.6.5 ).

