### **Blood Sample Collection and Processing**

At the specified time points, approximately 6 mL of blood will be collected in the specified tube type(s), to be processed, aliquoted into duplicate transfer vials and frozen, to be shipped to the designated analytical laboratory. Refer to the study protocol for blood sample collection time points.

Blood must be centrifuged, separated and frozen within 2 hours of collection. Specimens must be stored frozen at -70°C (preferred) or -20°C (acceptable) at each study site until shipped on dry ice to the designated analytical laboratory.

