#### For serum blood collection

Serum Tube, Increased Silica Act Clot Activator, Silicone-Coated Interior

Red Top Vacutainer

BD Catalogue 366430

*Abbreviated Title: ONC201 in advanced cancers*  
*Version Date: 06/17/2020*

Tube Size: 16 X 100

Draw Volume: 10mL

For serum aliquot storage

Wheaton 2mL Ext FS CryoElite

Yellow Cap Patch Sterile

Wheaton Catalogue W985866

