### **Collection of Blood**

Check the expiration dates on the vacutainer tubes before collecting blood. If the tubes have expired, discard them. Do not substitute another brand of collection tube. Prepare the blood collection tubes by affixing the barcode labels to each tube before collecting specimens from the subject.

Using standard aseptic venipuncture techniques, draw the blood sample into the specified collection tube. For time points requiring both plasma and serum blood draws, the plasma sample should be drawn first. Remove tourniquet as soon as blood flow into the first vacutainer tube is established; excessive use of tourniquets can lead to hemoconcentration and falsely elevated results. Ensure each vacutainer is full to provide accurate blood:additive ratios. Mix blood tubes by gently inverting each tube 5 times. On the barcode label, clearly print with a black permanent marking pen the study number “XXX”, patient ID number, the date and time of the blood draw (hours and minutes). Enter the information on the Patient-Specific Specimen Collection Log and maintain the log in the Patient source records.

Place the full blood collection tube(s) into a resealable clear biohazard bag. Arrange prompt pick up by, or delivery to, the local laboratory since blood must be processed and frozen within 2 hours of collection.

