### **15.6.3 Serum Processing**

After filling the tubes, let the tubes stand at room temperature until a clot has formed in the red top tube (approximately 30 minutes). Centrifuge the tube at 1500 g (3000 rpm) for 15 minutes until the serum and the cells are well separated. Label 2 yellow cap transfer vials lengthwise with the appropriate barcode labels indicating “serum (red)”. Clearly print the study number “Study XXX”, the patient ID number, date and time of the blood draw. Transfer ~1.5 mL of serum into each of the 2 yellow top transfer vials labeled “serum (red)”.

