### **Storage Instructions**

The clinical site laboratory is responsible for proper storage of the samples. Do NOT store plasma/serum specimens in a frost-free refrigerator-top freezer--results may be affected by temperature variation during the freezer cycle. Store in a freezer with minimum -20°C or preferably -70°C. Take all precautions to ensure the specimens remain frozen at the study site.

Duplicate aliquots of plasma and serum specimens will be prepared. One set of aliquots is to be kept stored frozen at the clinical site laboratory, and the second set is to be shipped according to this procedures manual.

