### **Preparing Tumor Sections for Shipping**

The tumor section slides should be shipped at room temperature (RT) to the Tumor Specimen Repository. Samples on glass or plastic slides must be adequately cushioned. Place the slides in a primary receptacle such as a slide box. Place this primary receptacle into a secondary leak-proof sturdy outer container or flexible-envelope packaging. The shipment must be packaged in compliance with IATA Packaging Instruction 650 for shipment of non-infectious human specimens. Use of the FedEx Clinical Pak is an option. Indicate the # of boxes shipped, and their total weight. Select 'Overnight Service', or other appropriate service assuring delivery within 24 hours.

One aliquot of plasma should be shipped to XenoBiotic Laboratories while the duplicate aliquot is shipped to Scisafe. Both the serum aliquots and tumor slides should be shipped to Scisafe.

*Abbreviated Title: ONC201 in advanced cancers*

*Version Date: 06/17/2020*

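### Table 5 omits the clotting step that Appendix F requires for the red-top serum tubes, and Appendix F contradicts itself on fill volume and on the plasma back-up aliquot

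*Combined protocol and SAP*

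**What the plan says.** Section 5.4.2 refers staff to Table 5 (section 5.5) for collection and storage. In the Plasma/Serum part of that table, the M30/M65 and TRAIL rows each take 6 mL into a red-top tube, and the spin is the first physical processing step: "Centrifuge the filled red top tube at 1500 g (3000 rpm) for 15 minutes until the plasma and the cells are well separated". The product is then aliquoted as serum: "Transfer ~1.5 mL of serum into each of the 2 yellow top transfer vials labeled".

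Appendix F covers the same samples. Section 15.6.3 tells the laboratory to "let the tubes stand at room temperature until a clot has formed in the red top tube (approximately 30 minutes" and only then to spin, with separation of serum, not plasma, as the end point. The red-top tube listed under Serum Sample Supplies contains a clot activator.

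On volume, Appendix F says "approximately 6 mL of blood will be collected in the specified tube type(s", which agrees with section 5.4.2 and Table 5. Its supply lists give "Draw Volume: 10mL" for both the lavender-top and the red-top tube, and Collection of Blood adds "Ensure each vacutainer is full to provide accurate blood:additive ratios".

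On the duplicates, Storage Instructions says "One set of aliquots is to be kept stored frozen at the clinical site laboratory" and has the other set shipped; this covers plasma and serum. The last paragraph of Preparing Tumor Sections for Shipping sends one plasma aliquot to XenoBiotic and its duplicate to Scisafe.

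**The concern.** A technician who follows Table 5 to the letter spins a clot-activator tube without the wait that Appendix F requires, and labels the result serum. Nothing in the two red-top rows points to section 15.6.3 for processing, although Table 5 does cross-refer where that is wanted: the germline DNA row sends the reader to Appendix D. Apart from tube colour, the spin sentence is the same as the one in the lavender-top plasma row, which suggests that it was carried over.

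Section 5.1 names TRAIL, M30 and M65 as the serum markers of apoptosis. Section 10.4.9 lists apoptosis markers among those whose differences from baseline, at cycle 1 and at cycle 2, will be related to PFS and compared between responders and non-responders. If a patient's baseline tube is handled one way and a later tube another way, that difference mixes handling with biology. The fill conflict raises the same question for the red-top tubes and also touches the PK plasma. The aliquot conflict decides whether any plasma remains at the site. A sample from a past visit cannot be drawn again.

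**Working it through.** This is mainly a comparison of texts, with some arithmetic on times and volumes. The plan gives no figure of its own to reproduce here.

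**1. Clotting (Table 5 against Appendix F)**
- Red-top rows, Table 5: collect, label, spin 15 minutes to separate plasma, aliquot as serum. No standing time is given.
- Section 15.6.3: stand about 30 minutes until clotted, spin 15 minutes to separate serum, aliquot as serum.
- Lavender-top PK tube: Table 5 and section 15.6.2 give the same spin instruction, and neither has a clotting step. The conflict is therefore confined to the two serum rows.
- Time check: 30 + 15 = 45 minutes. Both documents allow 2 hours from collection to freezing, which leaves 120 − 45 = 75 minutes for transport and aliquoting. The clotting step fits under Table 5's own limit.

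**2. Fill volume (inside Appendix F)**
- Collected about 6 mL; tube draw volume 10 mL; tube to be full.
- Fill = 6 / 10 = 60%, which is 4 mL short. With the listed tubes, the collected volume and the fill rule cannot both be met.
- Only if 6 mL is actually drawn into a listed 10 mL tube is the additive at 10 / 6 = 1.67 times its intended concentration.
- The aliquots need 2 × 1.5 = 3.0 mL, that is 50% of a 6 mL draw or 30% of a 10 mL draw. This does not show which volume was meant.

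**3. What filling the tubes would cost**

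Section 5.4.2 caps research blood at 40 mL per time point. I take the red-top entry as two 6 mL tubes, as in Table 5.
- Day 1 of later cycles, as listed: 8 (immune) + 10 (circulating tumor cells and cell-free DNA) + 4 (cytokines) + 12 (red-top) = 34 mL.
- Same visit with two full 10 mL red-top tubes: 8 + 10 + 4 + 20 = 42 mL, which is 2 mL over the cap.
- C1D1 before dosing, as listed: 8 + 10 + 10 (germline) + 4 + 12 + 6 (PK) = 50 mL, already over the cap; counting one red-top tube only, 44 mL. The baseline list therefore needs a look whichever tube is chosen.

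**4. Duplicate aliquots (inside Appendix F)**
- Storage Instructions: two plasma aliquots, one kept and one shipped.
- Shipping paragraph: two plasma aliquots, both shipped, to different laboratories. None is left at the site.
- Serum: "Both the serum aliquots and tumor slides should be shipped to Scisafe" can mean both duplicate serum aliquots, or serum aliquots as well as slides. Under the second reading there is no conflict with keeping one serum set.

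**The case against.** The best defence is that Table 5 is the short form and Appendix F the full one. Table 5 does not forbid clotting, calls the product serum, and leaves time for it; the tube in Appendix F has a clot activator. The same laboratory group is on call to receive these samples, so practice may well be uniform, and a uniform practice creates no difference between visits. The assays are exploratory and run on selected patients. All of this stands, and it limits the consequence. It does not remove the omission: no text ranks one instruction above the other, and the table to which staff are sent is the incomplete one.

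Several stronger readings are tempting but not supported:
- That following Table 5 fails to produce usable serum. This is an inference; the documents state no effect of unclotted spinning on these assays.
- That all three conflicts are Table 5 against Appendix F and cover PK. Only clotting is, and it excludes PK. The volume agrees at 6 mL in both places; the tube and fill conflict and the aliquot conflict lie within Appendix F.
- That every tube carries 1.67 times the additive. Table 5 gives no catalogue number or draw volume, and a partial fill is only one way out of the conflict.
- That up to 78 patients are affected at every cycle. Section 10.4.9 names only the cycle 1 and cycle 2 comparisons, and 78 is a ceiling given selective testing.
- That a failed shipment loses the time point. The two plasma aliquots go to different laboratories, and the serum instruction is ambiguous.
- That the serum destination conflicts. The address in Table 5 sits at a broken table cell, and some Appendix F text is not in the version available, so this cannot be judged.

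**Conclusion.** The point holds in limited form. Table 5's two red-top rows leave out a step of about 30 minutes that section 15.6.3 requires for the same tube type, and name plasma where Appendix F names serum. Separately, Appendix F gives two sets of instructions that cannot both be followed: about 6 mL into full 10 mL tubes, and one plasma aliquot set kept while both aliquots are shipped.

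The reach is exploratory serum markers and PK samples only. A distortion of the changes from baseline in section 10.4.9 requires that clotting or fill differ between visits of the same patient; the documents make that possible but do not show that it happens. No primary or secondary endpoint, sample size or error rate is affected. A conflict over the serum aliquots or the serum destination is not established. This is a minor correction, worth making because it is nearly free.

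**What to change.** 1. In both red-top rows of Table 5, insert the section 15.6.3 clotting step or refer to that section, and change plasma to serum in the spin sentence.
2. Make tube draw volume and collected volume agree across section 5.4.2, Table 5 and Appendix F. Tubes with a 6 mL draw would add no blood; keeping 10 mL tubes means revising the volumes and rechecking the 40 mL limit, which the C1D1 list appears to exceed already.
3. Reconcile Storage Instructions with the shipping paragraph, so that it is clear whether a plasma back-up stays on site. The documents do not show which was intended, so the sponsor must decide. At the same time, reword the serum sentence so that it has one meaning.
4. For samples already banked, record where possible whether the tube was clotted and how full it was, so that section 10.4.9 comparisons can be restricted to like-handled pairs.

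The cost is a few lines of procedure text and possibly a catalogue number. No visit or assay is added, and the extra 30 minutes fit within the existing 2-hour limit.
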